3 STUDY DESIGN

This study is a randomized, CAU-comparator, unblinded clinical trial of an in-home multidisciplinary intervention, *CAPABLE Transitions*, designed to help older adults successfully transition to their homes following hospital or post-acute care facility discharge. We plan to conduct this study for three years and to recruit 60 adults (36 in the intervention and 24 in the CAU arms) aged 65 years and older with and without dementia recently discharged from a hospital or post-acute care facility and admitted to a CHHA. Prior to randomization, we will stratify the 60 participants based on the presence or absence of moderate or severe cognitive impairment. *CAPABLE Transitions* consists of an OT-led multidisciplinary team in which the study OT (≤ 6 visits), RN (≤ 5 visits), and handyworker (≤ 2 visits) deliver an in-home intervention over three months. Study staff will follow participants for six months with assessments occurring at study enrollment as well as three and six months —following hospital or post-acute care facility discharge.

Our pilot study's primary outcomes relate to the feasibility of the study and include study recruitment and retention, fidelity to and perceived benefit of the intervention, and data completeness. The pilot study's secondary outcomes are to obtain preliminary data on home time, quality of life, and health care utilization at three and six months following hospital or post-acute care facility discharge.

4 SELECTION AND ENROLLMENT OF PARTICIPANTS

4.1 Inclusion Criteria

This study's target population is older adults living in an urban area who are admitted to a CHHA after discharge from a hospital or post-acute care facility. To participate in the study, with few exceptions (e.g., active cancer treatment, terminal diagnosis), there will be no restrictions based on sex, health status, or medical conditions, and all of the following inclusion criteria must be met:

- admitted to CHHA following a hospitalization or post-acute care facility stay (if not referred from CHHA, we will collect data on where patient referral is from)
- live in the Rochester, NY region
- aged 65 years or older
- English-speaking
- agree to study participation

We will deliver this intervention within a CHHA and with CHHA clinicians to enhance the scalability and the ease of dissemination if *CAPABLE Transitions* is effective. However, it is acceptable if patients have been admitted and then discharged from CHHA within the screening timeframe, or if participants may be working with other CHHA (staff such as PT or OT) and do not currently have an assigned CHHA registered nurse.

CHHA clients, regardless of their cognition, will have the option to include a study partner that may live with the study subject and be a primary caregiver to the study subject. Study partners may attend home visits and intervention sessions and be available via phone to answer questions from the research assistant. If needed, they must be available for other information via phone to be obtained from study staff. They may be asked general questions (e.g., age, sex) and about their relationship to the study participants and the participant's daily functioning, wellbeing, and health services use.

4.2 Exclusion Criteria

We will exclude potential participants from study participation who do not satisfy all of the inclusion criteria or meet any of the following exclusion criteria at baseline:

- plan to move within one year
- has a terminal diagnosis (e.g., <1 year life expectancy, in hospice)
- receiving active cancer treatment (active treatment includes surgery or a course of radiation or chemotherapy; it does not include long-term maintenance treatment such as daily hormonal treatment of prostate cancer)
- inability or unwillingness of individual or legal guardian/representative to give written informed consent.
- has been discharged to home from a hospital or post-acute care facility for more than 28 days
- are COVID-19 positive, have suspected COVID-19 infection, or resides with a person who is COVID-19 positive or has suspected COVID-19.

4.3 Study Enrollment Procedures

We will recruit older adults newly admitted to UR Medicine Home Care following discharge from a hospital or post-acute care facility. UR Medicine Home Care is a CHHA that provides services to a six-county region in Upstate New York.

- **Identification:** The CHHA has clinical teams based on geographic region. The study OT and RN will be on the same CHHA team, which will be assigned to a region in Monroe County, NY that includes the Rochester region. The study RN and OT will regularly screen all of their CHHA intakes to identify potential study participants (e.g., discharged from post-acute care facility, does not have a terminal condition). The study RN and study OT will ask clients passing the initial screen if they are interested in participating in our research study. The study RN and OT will also offer participants a recruitment brochure to introduce and provide information to home health patients if they are interested. For residents indicating an interest to participate in the research study and agree to have a study staff member visit them to provide more information, the study RN, OT, and CRC will work together to schedule an in-person screening visit that is convenient to the potential participant. In addition to the URMHC interventionists recruiting participants among their new admissions, we will contact potentially eligible URMHC clients who have indicated that they are interested in participating in research when they complete the new consent process via URMHC. This new consent process is for ALL URMHC patients admitted to URMHC services in which they can "opt in" or "opt out" of being contacted by a UR researcher if there is a study they qualify for. Only patients who have consented will be contacted by the CRC.
- **Study sample representativeness:** At each stage of the screening and recruitment process, we will document the proportion of CHHA clients who are not eligible for our study, are not interested in participating in our study, or are lost to follow-up. For these CHHA clients we will only keep basic demographic information such as age, sex, and race and ethnicity to allow us to track those who do and do not participate in our study; those older than 89 will be grouped in a 90+ age category. We will also utilize ICD-10 codes as part of the

screening process for the CHHA to help us identify participants that have dementia or cognitive impairment. However, we will not base our recruitment criteria or numbers based on this dementia category but will prioritize people with dementia. This information will help us determine the representativeness of our study sample and to examine whether there are subgroups that are unlikely to participate in the study (in which case, we made need to bolster recruitment efforts for certain subgroups).

- **Consent procedures:** As part of the consent process, study staff will systematically assess capacity for consent with a series of open-ended questions administered to the potential participant that follows explanation of the study (see Determination of Consent Capacity Form). These questions will address the participant's knowledge and understanding of the study's objectives, the voluntary nature of participation, ability to withdraw at any time, and possible risks and benefits of participation. For those unable to demonstrate capacity for consent, we will seek to obtain surrogate consent. Surrogate consent for dementia research is widely accepted by the general public,^{54, 55} and we will only enroll older adults with a surrogate consent if the older adult also assents to participate in the study and the surrogate consenter is able to demonstrate capacity for consent. We will not enroll any older adult who is unable to demonstrate capacity to provide informed consent if they do not have surrogate consent available. Although we will not enroll these older adults, we will compensate them with \$10 for completing the screening procedures.
- **Randomization:** Immediately following termination of the baseline assessment interview, study staff will randomly assign participants via a stratified random permuted block method.¹ Randomization will be stratified based on cognitive impairment status (moderate/severe cognitive impairment present: MMSE score ≤ 20 ; moderate/severe cognitive impairment absent: MMSE ≥ 21).^{44, 45, 86} Block randomization will then occur within each strata to ensure appropriate allocation to the treatment and CAU groupings. REDCap⁵⁶ will track the randomization groupings.

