1 STUDY OBJECTIVES

1.1 Primary Objective

This study's primary objective is to serve as a feasibility study of an intervention to assist older adults in the hospital or post-acute care facility-to-home transition and to test and refine procedures as they relate to:

- screening, enrollment, and retention of study participants
- fidelity to and perceived benefit of the intervention
- data completeness with regard to our intermediate and primary outcomes

Achieving this objective will inform the development of a larger clinical trial. This larger clinical trial will test the hypothesis that, among older adults discharged from hospitals or post-acute facilities (e.g., inpatient rehabilitation facilities and skilled nursing facilities) and admitted to a CHHA, those who receive *CAPABLE Transitions* will spend more days alive in their homes, have a higher quality of life, and have decreased utilization of emergency department, acute medical, and SNF care compared to older adults who receive CHHA CAU.

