9 STATISTICAL CONSIDERATIONS

9.1 General Design Issues

This study is a randomized, CAU-comparator, unblinded, 60-subject clinical trial of an OT-led in-home intervention designed to help older adults successfully transition to their homes following a hospital or post-acute care facility discharge. This research project is designed to be an iterative pilot study whose primary objective is to examine the feasibility of the *CAPABLE Transitions* intervention and the assessment of the study's intermediate and primary outcomes. Guided by research staff experiences, feedback from the study interventionists and participants, and our treatment fidelity data, we will continually seek to enhance and optimize the study protocol and procedures to improve recruitment. Such modifications could include adjustments to the intervention schedule or content or updates to our recruitment and retention process.

Given the focus on feasibility rather than hypothesis testing, this study is not blinded. This lack of blinding will enable the study CRC, research assistant, and/or PI to work closely with the study interventionists and treatment group participants to identify ways to enhance the study and its procedures.

Our analyses will largely consist of univariate statistics to examine the proportions and means and variance of the primary and secondary outcomes listed below and in Table 3.

Primary outcomes:

- screening, enrollment, and retention of study participants
- fidelity to and perceived benefit of the intervention
- data completeness with regard to our intermediate and primary outcomes

Secondary outcomes (at three and six months following hospital or post-acute care facility discharge):

- home time
- quality of life
- health care utilization

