9.4 Outcomes

9.4.1 Primary Outcomes

The primary study outcomes consist of the feasibility measures listed below.

- 1) Screening, enrollment, and retention of study participants: We will conduct univariate analyses to evaluate how many CHHA participants we screened, how many enrolled, and how many successfully finished the study.
- 2) Fidelity to and perceived benefit of the intervention (at three and six months):
 - a. To assess fidelity to the intervention, study staff will examine audio recordings of the intervention sessions and in-between session procedures (e.g., handyworker work order completed) and score whether the OT/RN completed the critical components associated with the intervention session. We will score completion of the critical components as "yes" or "no" and will then conduct univariate analyses to examine OT/RN adherence to the study protocol for the intervention sessions.
 - b. To evaluate perceived benefit of the intervention, study staff will conduct interviews at three and six months to obtain survey responses to Likert item scales on *CAPABLE Transitions* perceived benefit and burdensomeness to study participants. We will analyze these Likert item responses with univariate statistics. For narrative feedback, we will examine individual participant quotes and reported concerns for which we will not conduct

statistical analyses.

- 3) Data completeness with regard to our primary and intermediate outcomes at three and six months: We will use univariate statistics to examine the proportion of the CAU and intervention group participants who have information on our primary (i.e., home time, quality of life, health care utilization) and intermediate (e.g., timing and frequency of medical appointments, frequency of communication with medical providers, medication adherence, anxiety and depressive symptoms, physical functioning, home hazards, fear of falling, mobility, self-efficacy, pain) outcomes.

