If in answering these questions the participant is unable to demonstrate an understanding or appreciation of the issues, research staff and the participant will further review the consent form and repeat the pertinent questions. Participants who achieve a demonstrated understanding of the study will be determined to have capacity to provide informed consent. For those who do not, research staff will attempt to identify a legally authorized representative (LAR; see Section 7.3.1 for definition of LAR) who also will need to demonstrate capacity to provide informed consent prior to signing the informed consent document. If the older adult is unable to provide informed consent and does not have a LAR able to provide informed consent, we will thank them for their time with \$10 for completing the screening and procedures and inform them that they are not eligible for the study. Participants' answers are tracked on a Determination of Consent Capacity Form that is kept with the research record as documentation of the consent process. For participants/LARs unable to provide informed consent, however, we will document the reason for study ineligibility on the Determination of Consent Capacity Forms. On these forms, we will not include any personal identifiers, but rather will use a screening ID number to track completion of these forms for participants and, if applicable, LARs. For participants and LARs unable to provide informed consent and who are not enrolled in the study, the screening ID number will not be linked to any personal identifiers. For enrolled participants who thereby demonstrate and provide informed consent or who have an LAR that provides informed consent, however, we will link these screening ID numbers with an assigned study-specific ID number that can be linked to identifiers we are collecting for the study. We will not keep any identifiable information for older adults/LARs who do not or are unable to sign consent to participate in our study. Rather, we will only keep basic demographic information such as age, sex, and race and ethnicity to allow us to track those who do and do not participate in our study; those older than 89 will be grouped in a 90+ age category.

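### Apart from inability to consent, the plan does not provide for recording why screened clients are ineligible or decline, so the pilot can locate recruitment losses but has no systematic data on their causes

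*Combined protocol and SAP*

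**What the plan says.** Section 1.1 lists "screening, enrollment, and retention of study participants" first among the procedures that the pilot is to test and refine. Section 9.1 adds that "we will continually seek to enhance and optimize the study protocol and procedures to improve recruitment".

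Section 4.3 (Study sample representativeness) says that at each stage of screening and recruitment the plan is to "document the proportion of CHHA clients who are not eligible for our study, are not interested in participating in our study"; a third group is those with whom contact is lost. The next sentence sets what is retained: "For these CHHA clients we will only keep basic demographic information such as age, sex, and race and ethnicity". The stated use is to judge representativeness and to find subgroups unlikely to take part.

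Section 11.2 states the rule again in a privacy setting: "We will not keep any identifiable information for older adults/LARs who do not or are unable to sign consent to participate in our study". The demographics-only sentence follows directly. The same section makes one exception. For participants or representatives unable to give informed consent, "we will document the reason for study ineligibility on the Determination of Consent Capacity Forms", under a screening ID that is not linked to identifiers.

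The planned analysis in Section 9.4.1, item 1, is univariate, to "evaluate how many CHHA participants we screened, how many enrolled, and how many successfully finished the study".

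**The concern.** A pilot meant to refine recruitment needs to know what is costing it participants. *Not eligible* can mean a fixed fact such as age or language, a criterion that a later trial might reconsider such as a planned move within a year, or a logistical failure such as not completing enrolment within 28 days of discharge. *Not interested* can reflect visit burden, unease about home modifications, or reluctance to be randomised. Each points to a different change in procedure. Demographics show who was not enrolled, not why.

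At stake is the usefulness of a primary feasibility outcome. The larger trial would inherit a recruitment yield with little structured evidence on how to raise it. The loss is also permanent: no identifiers are kept on these people, so a reason not noted at the time cannot be collected afterwards.

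**Working it through.** The documents give no figure that depends on this point, so there is nothing to reproduce. The check is a comparison of sections, followed by an illustration of scale.

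**1. Which reasons have a place to be recorded?** Section 4.1 lists 5 inclusion criteria and Section 4.2 lists 6 exclusion criteria, 11 in all.

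- Agreement to take part (4.1), and unwillingness to consent (part of one bullet in 4.2), fall naturally under *not interested*. No reason for declining is provided for.
- Inability to consent (the other part of that 4.2 bullet), including the case where no representative can consent, has its reason documented under Section 11.2.
- That leaves 11 − 2 = 9 bullets that share the single *not eligible* category. Four are inclusion criteria: home health admission after a hospital or post-acute stay, region, age and language. Five are exclusion criteria: planned move, terminal diagnosis, active cancer treatment, more than 28 days since discharge, and COVID-19.

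**2. What can the planned data show?** Section 4.3 gives disposition at each stage. Ineligibility can therefore be separated from lack of interest, and losses at intake from losses at the in-person visit. Within *not eligible*, the 9 criteria cannot be told apart. Sections 4.2 and 6.2.1 both exclude clients not enrolled within 28 days, so a scheduling failure falls in the same category as age or language.

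**3. How does the plan treat reasons elsewhere?** Section 8 separates participants who stop the intervention satisfied from those who stop dissatisfied. Reasons are distinguished at exit from the intervention, but apart from consent incapacity there is no counterpart at entry.

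**4. Scale, under an assumed yield.** Target enrolment is 60 (Section 9.2). The share of screened clients who enrol is not given; assume 10% to 30%.

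- Screened = 60 / yield: 60 / 0.30 = 200, and 60 / 0.10 = 600.
- Not enrolled: 200 − 60 = 140, and 600 − 60 = 540.
- The 95% half-width for a reason behind 25% of losses is 1.96 × √(0.25 × 0.75 / n). At n = 140 it is 0.072, or 7.2 percentage points. At n = 540 it is 0.037, or 3.7 points.

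These half-widths assume a usable reason for every non-participant, so *none given* entries would widen them. The 140 to 540 also include people whose consent incapacity Section 11.2 already documents, so the number with no recorded reason would be somewhat smaller.

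**The case against.** The strongest reply is that the retention sentence is a privacy rule, not a ban on reasons. In Section 11.2 it follows directly from the statement that no identifiable information is kept on people who do not sign, and the words *such as* leave the list open. A reader might infer that the protocol forbids keeping reasons. The documents do not clearly support that: an anonymous tally is unplanned rather than plainly prohibited. What stands against the reply is that *such as* qualifies demographic information, and that staff following the word *only* could reasonably record nothing more.

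A second reply is that the team will learn why people decline anyway. Section 9.1 says that changes will be guided by staff experience and by interventionist and participant feedback, and the study RN and OT both screen clients and deliver the intervention. It would therefore be too strong to say that the team will know nothing about the causes. This channel is real but informal. It gives no counts, and no provision is made to report it.

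A third reply concerns consent. Codes for terminal illness, cancer treatment or COVID-19 would be health information about people who never consented, and Section 7.3.1 treats collection of protected health information as research requiring prior documented consent. Asking why someone declined, often by that person's own clinician, also sits close to the same section's concern with undue influence. Both points stand, and they shape the fix.

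**Conclusion.** The point holds as a gap in provision. Apart from inability to consent, the plan makes no arrangement to record the failed criterion or the reason for declining, and its retention wording can be read as excluding both. This limits the first-listed primary objective. It does not affect participant safety or the other outcomes.

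Two wider conclusions might be drawn, and neither is supported. One is that every eligibility criterion disappears into a single category: refusals have their own category and consent incapacity has its own form, which leaves 9 of the 11 bullets pooled. The other is that the pilot cannot describe its losses: stage and broad disposition are already documented.

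The text comparison needs no assumption. The figures of 140 to 540 non-participants and about ±7 to ±4 points rest wholly on the assumed 10% to 30% yield and on complete recording, and they only illustrate scale. The change is worth making because it is small and because unrecorded reasons cannot be recovered.

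**What to change.** - **Sections 4.3 and 11.2:** extend the retention wording to basic demographics plus one coded, de-identified reason. The reason is the first failed criterion from Sections 4.1 and 4.2 or, for those who decline, the main reason the client volunteers. Allow *none given*, and state that the clinician does not probe.
- **Storage:** hold the reason as an anonymous tally or under an unlinked screening ID of the kind Section 11.2 already uses. Group health-related criteria if the IRB requires it. Section 11.2 describes that ID for the consent-capacity forms, so the amendment should say what applies to clients screened out earlier at intake.
- **Section 9.4.1, item 1:** tabulate the stage-by-stage losses that Section 4.3 already documents by reason, with numbers and proportions.

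The cost is seconds of staff time per screened client and an IRB amendment that expressly covers limited de-identified data on people who did not consent. Some entries will be *none given*. No visit, identifier or further contact with clients is added.
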